Based on motor learning theories, recent studies have demonstrated that **intensive, repetitive, task-oriented therapies** (IRTT) can help a paretic limb “relearn” how to perform movements that were lost after brain damage^{12,13}. The same principle can be applied to children with CP that do not have to relearn given movements but rather learn how to perform them in a functionally adequate manner¹⁴⁻¹⁶. The mechanism by which functional recovery and motor learning are believed to occur is through the enhancement of neuronal plasticity¹⁷. A motor learning study in humans has shown that 300 to 800 repetitions per session are needed for motor learning to occur¹⁸ yet, only an average of 32 repetitions of upper-limb movements is achieved during conventional therapy¹⁹. There is robust evidence that IRTT can improve motor and functional ability of the hand²⁰. While there is limited evidence for the efficacy of most approaches to hand rehabilitation in CP²¹, some studies have demonstrated that children with hemiplegia may benefit from intensive unimanual practice^{14,15}. One approach that has demonstrated promising outcomes in hand rehabilitation in children with CP is constraint-induced movement therapy (CIMT)²²⁻²⁷ since it involves restraining the non-paretic limb while providing intensive targeted practice with the paretic limb. However, the use of CIMT is fundamentally flawed when done in children²⁸ and, as such, must be modified; and the approach can lead to temporary deficits in QoL during the prolonged treatment period (use of a cast). Consequently, novel approaches that enable IRTT need to be implemented in children with CP. Robotic devices have become a very important area of research because of their capacity to achieve IRTT^{29,30}. While the use of robotic-assisted therapy (RAT) to improve grasping and fine motor control has yet to be implemented in children with CP, RAT has been demonstrated as an effective intervention in children with CP for gait rehabilitation³¹⁻³⁷ and reaching movements^{38,39} suggesting that using the RAT could improve hand function in this population. In the proposed study, we will assess the effectiveness of the Amadeo®. The device has been shown to improve manual dexterity in stroke survivors. The computer-controlled device maintains patients’ forearm in a secure position using Velcro straps. The patients fingertips are then attached to the robotic device using mild adhesive tape (like a band aid). Patients then have to control interactive games displayed on the screen using their fingers.

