Briefly describe study design and anticipated enrollment, i.e., number of subjects to be enrolled by researchers study-wide and by Partners researchers. Provide a brief summary of the eligibility criteria (for example, age range, gender, medical condition). Include any local site restrictions, for example, “Enrollment at Partners will be limited to adults although the sponsor’s protocol is open to both children and adults.”

A sample of 10 children with CP with no major orthopedic or neurological complications that could interfere with the robot-assisted training will be recruited in the study. This sample size was calculated for an F test with an effect size of 0.4, an alpha of 0.05, a beta of 0.80, a correlation coefficient between repeated measures of 0.7, and an attrition rate of 20%. A study clinician will screen potential subjects. Screening will include a standard history and physical exam to ensure subjects meet all entry requirements after consideration of inclusion and exclusion criteria. Specifically, [name], the study physician, will assess all subjects' suitability for using the Amadeo.

Inclusion criteria:

- Diagnosis of CP with upper-limb impairment
- 6 to 18 years of age.
- Manual Ability Classification Scale Level II or III.
- Ability to communicate pain or discomfort.

Exclusion Criteria:

- Recent use of upper-limb robotic-assisted training within the last 3 months.
- Contraindication to robotic-assisted manual training such acute and pronounced pain symptoms despite conventional pain therapy of the upper-limb, lack of compliance, high-grade ataxia, advanced osteoporosis, and fractures of the upper-limb.
- Modified Ashworth Scale (MAS) of 4 in the upper-limb.

Briefly describe study procedures. Include any local site restrictions, for example, “Subjects enrolled at Partners will not participate in the pharmacokinetic portion of the study.” Describe study endpoints.

All study procedures will take place in the Motion Analysis Laboratory at Spaulding Rehabilitation Hospital, Boston, Massachusetts, USA. Spaulding Rehabilitation Hospital is an affiliated hospital of Harvard Medical School.

Assessments

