Once the children are enrolled in the study, they will undergo a baseline assessment before undertaking a 6 weeks/18 sessions RAT program. Once training is completed, the children will undergo a final assessment. Finally, a follow-up assessment will be performed one month after the end of the RAT program to evaluate retention in the quality of life.

The follow up assessment will be performed 4 weeks after the end of the intervention and will consist in the cerebral palsy Quality of Life Questionnaire, which it will be provided to the subjects and they will be asked to fill it out and return to us when completed by email or mail (note: the questionnaire does not include any identifiable information).

Clinical tests

Clinical tests will be conducted by a study staff before and after the intervention. Clinical testing should last about 1 hour and will include:

- Physical examination: we will gather measures of Range of Motion (ROM) and muscular strength for the upper extremities. Passive and active movements of the shoulder (flexion, extension, abduction and adduction), elbow (flexion and extension), radioulnar joint (pronation and supination), wrist (flexion, extension, abduction, and adduction), and fingers (flexion, extension, abduction, and adduction) will be assessed with a goniometer.
- Modified Ashworth Scale (MAS)^{48,49}: We will assess spasticity at the shoulder (flexion-extension); elbow (flexion-extension); radioulnar (pronation-supination), and wrist (flexion-extension).
- Quality of Upper Extremity Skills Test (QUEST): this standardized test is a validated and reliable tool to evaluate movement patterns and hand function in children with cerebral palsy. The QUEST evaluates quality of upper extremity function in four domains: dissociated movement, grasp, protective extension, and weight bearing.
- Box and block test⁵²: this test assesses unilateral gross manual dexterity. Children are seated at a table, facing a rectangular box that is divided into two square compartments. The individual is instructed to move as many blocks as possible, one at a time, from one compartment to the other for a period of 60 seconds.

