Describe explicitly the methods for ensuring the safety of subjects. Provide objective criteria for removing a subject from the study, for example, objective criteria for worsening disease/lack of improvement and/or unacceptable adverse events. The inclusion of objective drop criteria is especially important in studies designed with placebo control groups.

Subjects will be screened prior to and during enrollment for the presence of medical conditions that may contraindicate their participation.

FORESEEABLE RISKS AND DISCOMFORTS

Provide a brief description of any foreseeable risks and discomforts to subjects. Include those related to drugs/devices/procedures being studied and/or administered/Performed solely for research purposes. In addition, include psychosocial risks, and risks related to privacy and confidentiality. When applicable, describe risks to a developing fetus or nursing infant.

The robotic device that we propose to use in the study (i.e. the Amadeo® by TyroMotion) has been developed for adults and pediatric populations above 3 years of age (see device brochure). Training sessions will be always overseen by a study staff trained in the use of robotic systems for upper-limb training. The risks of using the Amadeo® include muscle soreness and fatigue, but no harmful adverse events have been reported with its use. Trained study staff will stretch the hand of the participants to minimize soreness. The Amadeo® is being used in another approved protocol that is taking place within the MAL (2015-P002107).

Subjects with CP are at higher than normal risk for falls and injuries from daily activities. Some of the proposed testing procedures will assess the subject's performance of activities of daily living. In general, subjects will be at no greater risk for falls or injury than when performing tasks in the home and community setting. Subjects will be under constant observation. Trained staff will be nearby to help in case of loss of balance. During training and when standing is not required, subjects will be seated on a comfortable chair.

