Describe the plan for monitoring the data to ensure the safety of subjects. The plan should include a brief description of (1) the safety and/or efficacy data that will be reviewed; (2) the planned frequency of review; and (3) who will be responsible for this review and for determining whether the research should be altered or stopped. Include a brief description of any stopping rules for the study, when appropriate. Depending upon the risk, size and complexity of the study, the investigator, an expert group, an independent Data and Safety Monitoring Board (DSMB) or others might be assigned primary responsibility for this monitoring activity.

NOTE: Regardless of data and safety monitoring plans by the sponsor or others, the principal investigator is ultimately responsible for protecting the rights, safety, and welfare of subjects under his/her care.

Approval of protocol, informed consent procedures, and recruitment will be obtained from the IRB during annual reviews. Monthly data and procedural reviews by the PI in consultation with study staff will be done to identify and ameliorate any potential safety issues. Any safety concerns about the equipment or protocol will be brought to the immediate attention of [name]. Study staff will conduct bimonthly audits to ensure compliance with regulatory standards for study documentation.

Describe the plan to be followed by the Principal Investigator/study staff for review of adverse events experienced by subjects under his/her care, and when applicable, for review of sponsor safety reports and DSMB reports. Describe the plan for reporting adverse events to the sponsor and the Partners' IRB and, when applicable, for submitting sponsor safety reports and DSMB reports to the Partners' IRBs. When the investigator is also the sponsor of the IND/IDE, include the plan for reporting of adverse events to the FDA and, when applicable, to investigators at other sites.

NOTE: In addition to the adverse event reporting requirements of the sponsor, the principal investigator must follow the Partners Human Research Committee guidelines for Adverse Event Reporting

Study staff will report any adverse event promptly to [name]. Adverse events reporting will be done according to Partners Human Research policy, and appropriate changes in procedure and protocol will be implemented to prevent reoccurrence. Remedial action to prevent reoccurrence of the event will be instituted prior to resumption of the study treatment.

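### The soreness, fatigue, skin irritation and bruising that the plan expects are left to unsolicited adverse event reports, with no systematic questioning and no planned tolerability summary

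*Combined protocol and SAP*

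**What the plan says.** - **Named risks.** Foreseeable Risks and Discomforts states: "The risks of using the Amadeo® include muscle soreness and fatigue, but no harmful adverse events have been reported with its use". The same section links skin irritation and mild bruising to the tape, electrodes, markers and skin preparation of the laboratory assessment. It also accepts that children may tire or be uncomfortable at any visit.
- **Handling.** Trained staff oversee every training session. Stretching, rest periods, hypo-allergic tape and constant observation are the stated precautions.
- **Capture.** Data and Safety Monitoring has staff report any adverse event promptly, under institutional policy, with monthly review by the principal investigator. It adds: "Remedial action to prevent reoccurrence of the event will be instituted prior to resumption of the study treatment".
- **Outcomes and analysis.** The clinical tests are range of motion, strength, the Modified Ashworth Scale, QUEST, Box and Block and the CP quality-of-life questionnaire; the laboratory study adds EMG and kinematics. The clinical analysis is a descriptive pre/post comparison of these measures. No safety or tolerability summary appears.
- **Follow-up.** The 4-week contact "will consist in the cerebral palsy Quality of Life Questionnaire", returned by email or mail. One of its seven domains covers pain and impact of disability in general.
- **Population.** Eligibility requires "Ability to communicate pain or discomfort". The Background says the use of robotic-assisted therapy "to improve grasping and fine motor control has yet to be implemented in children with CP".

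**The concern.** The plan predicts specific mild effects and enrols only children able to report discomfort, yet it schedules no occasion for asking about training-related effects. Mild, expected effects are the ones most easily left out of an unsolicited system, because staff may regard them as a normal part of training. The prompt in Data and Safety Monitoring asks which safety data will be reviewed; the answer refers to data and procedural reviews without naming any item, definition or grade.

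At stake is a result that a small single-group pilot can usefully describe: how many children had soreness, fatigue or a skin reaction, and how many sessions were shortened or stopped. These data cannot be reconstructed afterwards. Without them, the reassuring sentence about the device would be carried forward with little added evidence from a use that the plan itself calls not yet implemented in children with CP.

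**Working it through.** **1. The denominator.** The plan recruits "A sample of 10 children with CP with no major orthopedic or neurological complications". The basis is: "This sample size was calculated for an F test with an effect size of 0.4, an alpha of 0.05, a beta of 0.80", then "a correlation coefficient between repeated measures of 0.7, and an attrition rate of 20" per cent. I read the 0.80 as power. For a one-group repeated-measures F test with m measurements, sphericity assumed, lambda = n x m x f²/(1 − rho), with m − 1 and (n − 1)(m − 1) degrees of freedom. The plan does not state m.
- m = 3: n = 8 gives lambda = 8 x 3 x 0.16/0.3 = 12.8 and power 0.825 (n = 7 gives 0.753). Then 8/0.80 = 10, which matches.
- m = 2: n = 10 gives power 0.827, and 10/0.80 = 12.5, so 13, which does not match.

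The stated 10 is therefore reproduced with three measurements. The present point does not depend on this; it needs only 10 children starting and about 8 completing.

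**2. Exposure.** 10 x 18 = 180 training sessions if all complete; 8 x 18 = 144 from eight completers alone. These denominators suit soreness, fatigue and fingertip skin, since fingertips are taped in training. Sensor-related irritation and bruising belong to the laboratory assessments (baseline and final), so their denominator is children assessed, not 180 sessions.

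**3. Where each effect could be captured.**

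| Effect | Scheduled question | Other route | Planned summary |
|---|---|---|---|
| Soreness, fatigue (training) | None described | Unsolicited report; observation | None |
| Skin irritation, bruising (laboratory) | None described; past sensitivity is asked beforehand | Unsolicited report; observation | None |
| Any effect after the final assessment | General pain domain only | Family may contact staff | Questionnaire only |

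**4. What systematic asking would give.** For zero events in n children, the exact two-sided 95% upper limit is 1 − 0.025^(1/n).
- n = 10: 1 − 0.025^(1/10) = 0.308.
- n = 8: 1 − 0.025^(1/8) = 0.369.

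The first is the relevant one, because every child who starts training is exposed. As these effects are expected, zero is not the likeliest result. The chance of seeing at least one affected child among 10 is 1 − (1 − p)^10. For assumed true per-child rates p of 5%, 10%, 20% and 30%, it is 40%, 65%, 89% and 97%.

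**5. What unsolicited reporting gives.** Let s be the probability that an affected child is reported; the documents give no value. The reported proportion then estimates s x p. With zero reports in 10, the limit is s x p ≤ 0.308, so p ≤ 0.308/s. Only s = 1 recovers 31%; at s = 0.308 or less the limit on p reaches 100% and says nothing. Systematic asking is intended to bring s close to 1.

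**The case against.** The strongest reply is that safety capture exists. Any adverse event must be reported promptly, the principal investigator reviews monthly, trained staff watch every session, and the study coordinator monitors data and adherence at each step. That stands. A reader might infer that these effects are not recorded at all or that the pilot can report no tolerability result; the documents support neither. Spontaneous reports could be listed, withdrawals counted, and attended sessions recovered from per-session payments. The gap is in asking, grading and summarising.

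A reader might also infer that events after the last visit cannot be known. They are unsolicited, but families are given staff contact details and the questionnaire has a pain domain, although that domain does not attribute pain to training.

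Another tempting reading is that the remedial-action wording contradicts the handling of soreness and fatigue by stretching and rest. That is not shown: no length of pause is set, and rest or stretching could itself be the remedial action.

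Three further points limit the weight. The document is a summary form that invites brief answers, and the institutional adverse event policy is not available, so a session form or definition may exist elsewhere. Tolerability is not one of the two aims. The novelty statement concerns robotic hand training in CP; the device is described as developed for adults and for children above 3 years, and another protocol in the laboratory uses it in an unstated population. None of these supplies a planned question or a planned table.

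**Conclusion.** The point holds in limited form. The plan names the mild effects it expects, relies on unsolicited adverse event reports with monthly review to capture them, and commits to no systematic questioning and no safety or tolerability summary. Following it as written would yield a list of reports but no reliable rate.

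The scale is up to 180 training sessions, two laboratory assessments per child and a 4-week follow-up. Even with full ascertainment the precision is modest (0 of 10 leaves up to 31%), so the gain is an interpretable description, not proof of safety. The conclusion rests on the document as published; a session log held elsewhere would answer part of it. It does not invalidate either aim. It is a low-cost improvement that should be made before enrolment, because the data cannot be recovered later.

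**What to change.** 1. **Each training session:** staff already present log the child's reported soreness and fatigue before and after, fingertip skin appearance, active minutes completed, and whether and why the session was shortened or stopped.
2. **Laboratory assessments and follow-up:** record skin irritation and bruising at the two laboratory assessments, and add one adverse event question to the 4-week questionnaire mailing.
3. **Analysis:** add to the descriptive analysis under Clinical tests the number of exposed children (all who started, not only completers) and the number of sessions with each event. Give exact intervals for the per-child proportions. Sessions within a child are not independent, so report session counts descriptively.
4. **Clarification, at most:** ask the investigators to state how the remedial-action wording in Data and Safety Monitoring applies to the expected effects. The choice is theirs.

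**Cost:** about 1-2 minutes per session, so 180 to 360 minutes (3 to 6 hours) over 180 sessions, plus a brief skin check, one question, one table and a minor amendment. No extra staff or visits.
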